**SPECIFIC AIMS**

Concisely state the objectives of the study and the hypothesis being tested.

One of the goals of this proposal is to investigate if co-administration of rhIGF-1 with physiologic estradiol replacement to adolescent girls with AN will increase BMD more than estrogen monotherapy, and bone mass will approach that seen in healthy adolescent girls.

An additional aim for the prospective study is to determine whether co-administration of rhIGF-1 with estradiol to mimic the normal pubertal milieu:

- A) Stimulates bone formation through an IGF-1 mediated anabolic effect
- B) Increases bone density to a greater extent than estrogen monotherapy
- C) Improves bone mass accrual to approach that in healthy controls

Further more we will investigate if co-administration of rhIGF-1 with physiological estradiol replacement will improve bone microarchitecture and bone strength in girls with AN. In a cross-sectional study of adolescent girls with AN and healthy adolescent girls, we will determine whether:

- A) Cortical and trabecular bone density and microarchitecture at the ultradistal radius (non-weight bearing bone) and tibia (weight bearing bone) as assessed by HR-pQCT, and bone strength, as assessed by finite element analysis (FEA), are abnormal in AN compared to controls, and are associated positively with nutritional and hormonal predictors of bone mass, including BMI, body fat, fat-free mass, estradiol and IGF-1 levels

In a prospective study of adolescent girls with AN we will determine whether:

- B) Co-administration of rhIGF-1 with transdermal estrogen improves cortical and trabecular bone microarchitectural parameters (assessed by HRpQCT) and bone strength (assessed by FEA) more than estrogen alone to approach that in normal adolescent girls. Girls with AN receiving estradiol alone will have an increase in bone microarchitecture and strength versus baseline, but will not normalize compared to healthy controls
- C) Changes in IGF-1 levels are associated positively with changes in measures of bone density, microarchitecture and strength.

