  - b. 14-19: mild depression
  - c. 20-28: moderate depression
  - d. 29-63: severe depression
- (g) STAI: State Trait Anxiety Inventory questionnaire is a 40-item and four-point Likert scale self-report inventory assessing state and trait anxieties common in AN. (All subjects consent to standardized psychiatric tests, although they are treated as optional during the study. This component can also be completed at the screen visit, instead of the baseline visit.)

- (h) Activity Assessment: Habitual exercise and activity will be assessed using a standardized exercise questionnaire, which provides a good estimate of past year physical activity in adolescents (26, 27). (All subjects consent to the activity assessment, although it is treated as optional during the study.)
- (i) Bone Turnover Markers: Serum for PINP and C-telopeptide (CTX).
- (j) Calcium Metabolism: Blood for calcium, phosphorus, 25(OH) D, 1,25(OH)2D, PTH.
- (k) Hormonal Evaluation: Serum for IGF-1, IGFBP-3, SHBG, estradiol, leptin.
- (l) If not obtained at screening visit: Blood laboratory work for glucose, TSH, LH, FSH, potassium and hematocrit, and IGF-1. Medications will be withheld until laboratory results are received and assessed.
- (m) Bone Mass Density: lumbar spine (AP and lateral), hip, radius, whole body areal BMD, BMC and BA will be measured by dual energy x-ray absorptiometry (DXA: Hologic QDR 4500, Waltham, MA).
- (n) Body Composition: Whole body DXA will be performed to assess fat and lean mass.
- (o) Bone morphology, microarchitecture and strength will be determined at the ultradistal radius and distal tibia using HR-pQCT (Xtreme CT, Scanco Medical AG). Bone strength will be determined using FEA of HR-pQCT scan data (28).
- (p) Safety Evaluation: Urine or Serum HCG (to rule out pregnancy) and fasting glucose.
- (q) Thigh and abdomen MRI and an L4 MR spectroscopy will be performed to assess bone marrow fat. We will also add Pref-1 assessment to the already collected blood. This will only be repeated at 12 months for patients with anorexia nervosa.
  - a. This study is optional for AN subjects and non-optional for HC subjects

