- (j) Activity Assessment: Habitual exercise and activity will be assessed using a standardized exercise questionnaire, which provides a good estimate of past year physical activity in adolescents (26, 27). (All subjects consent to the activity assessment, although it is treated as optional during the study.)

(k) Two subtests, Vocabulary and Matrix Reasoning, from the Weschler Abbreviated Scale of Intelligence (WASI), a Color-Word Interference Test subtest from the Delis Kaplan Executive Functioning Scale (DKEFS), and the California Verbal Learning Test (CVLT). (All subjects consent to the cognitive assessments, with the intention that they will be completed to the extent that time, subject schedule, and circumstances allow during the visit)

6-month and 12-month (AN Subjects Only): will include all the baseline procedures but the bone age x-ray.

Eligible consented subjects will be allowed to have CT scans performed between the screening and baseline visits if scheduling conflicts arise with the baseline visit. This will allow the subject to obtain a baseline assessment of bone microarchitecture prior to the initiation of rhIGF-1 supplementation. In the event that a CT cannot be performed on the scheduled baseline visit date due to unforeseen issues, willing subjects will be able to return within a 1 week window for this test. DXA scans can also be completed at screening visit if not able to be performed at baseline visit. MR/MRS will be repeated at 12 month visit for patients with anorexia nervosa. We will also repeat the Pref-1 levels for those who enrolled in this optional part of the study.

1-month, 4.5-month, 7.5-month and 10.5 month visits (AN Subjects Only): Evaluations on these visits will include:

- (a) History and physical exam, including height and weight
- (b) Pregnancy test
- (c) Serum IGF-1 and glucose

3-month and 9-month visits (AN Subjects Only): Evaluations on these visits will include:

- (a) History and physical exam, including height and weight
- (b) Pregnancy test
- (c) Serum IGF-1 and glucose
- (d) Nutrition evaluation will be assessed by using 4-day food records for macro- and micronutrient intake (Nutrition Data Systems, version 4, Minneapolis, MN)
- (e) Activity assessment: Habitual exercise and activity will be assessed using a standardized exercise questionnaire. (All subjects consent to the activity assessment, although it is treated as optional during the study.)
- (f) Bone turnover markers and hormones

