Sample Size Determination: The study is powered to our primary endpoints, (i) change in lumbar spine BMD (specific Aim 1A), and (ii) change in trabecular bone density (specific Aim 3A) in girls with AN who receive estrogen and rhIGF-1 versus estrogen alone. **Specific Aim 1A:** The primary analysis for this Specific Aim and the study is to compare the change in BMD over time in subjects with AN randomized to receive rhIGF-1 and estrogen (n=50) with the corresponding change in estrogen treated subjects (n=50). Using data from our previous study, we found that the variance covariance matrix of the random effects model was as follows: variance-intercept 0.01056, variance-slope 0.001523, covariance -0.001, and the residual variance around each subject's trajectory 0.000533. Based on these parameters, with 100 subjects with AN (50 in each group), we will have an 80% chance of detecting a significant (p=0.05 two sided) difference in change in lumbar spine BMD between girls who receive estradiol and rhIGF-1 versus estradiol alone if the true difference in slope between the groups is 0.03 g/cm²/year. This is a medically significant difference in that lumbar spine BMD in adolescents with AN is about 0.08 g/cm² lower than that in healthy adolescents at baseline. Estradiol alone has a net effect of 0.02 g/cm².year in increasing bone density, so an additional effect of 0.03 g/cm² (with rhIGF-1) added to 0.02 g/cm² (from estradiol alone) would be a net effect of 0.05 g/cm²/year (from estradiol and rhIGF-1). This would allow girls with AN to catch up to healthy adolescents. The sample size calculation, which assumes a 20% dropout rate, is based on the methods described by Yi and Panzarella (38) using the program <http://hedwig.mgh.harvard.edu/biostatistics/node/35>. The same model can be used with covariates and possible mediators of treatment effects such as baseline nutritional status, body composition, hormonal status, exercise and pubertal maturation. We will also explore the possibility that effects of rhIGF-1 with estradiol persist after discontinuation of treatment by examining bone density 12 months after stopping therapy.

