Specific Aim 1B. We will analyze the impact of rhIGF-1 with estrogen (n=50) versus estrogen alone (n=50) on levels of the bone turnover markers, PINP and CTX, in girls with AN at 3, 6, 9 and 12 months using a repeated measures ANOVA. The primary planned analysis will be the difference in mean levels by treatment group during the 3, 6, 9 and 12 month observations. As for Specific Aim 1A, we will examine whether effects of combination therapy persist following discontinuation of therapy by examining these markers after 12 months of stopping therapy.

Specific Aim 1C. We will use the longitudinal model described above to compare the rate of bone mass accrual in girls with AN who receive rhIGF-1 with estrogen (n=50) with that seen in healthy controls (n=36). We expect the change in BMD in AN girls to exceed that in controls because of a “catch up” effect when rhIGF-1 is used with estradiol. We will control for multiple comparisons in our analysis when comparing against controls. Both unadjusted and multiplicity adjusted analyses will be presented.

Specific Aim 2A. In a cross-sectional design, we will compare the described HR-pQCT endpoints and bone strength (as assessed by FEA) in girls with AN (n=100) to those in healthy adolescents (n=36). We will use the Student t test when variables are normally distributed or when transformations can be performed to approximate a normal distribution; otherwise, we will use non-parametric tests such as the Wilcoxon rank sum test. Our preliminary data indicate lower trabecular bone density in 8 girls with AN compared with 6 controls (162 ± 27 vs. 209 ± 36 g/cm³, $p=0.02$). Based on these data, with 100 girls with AN and 36 controls in the study, we have >99% power for detecting a significant difference in trabecular bone density between the groups at an alpha level of 0.05. Another component of this specific aim is to determine the extent to which DXA parameters and possibly clinical parameters predict bone microarchitecture in the 100 adolescents with AN. This will help elucidate the role of DXA in the future clinical evaluation of adolescents with AN. Linear regression followed by regression modeling will be performed to determine hormonal, body composition, nutritional and exercise predictors of bone microarchitecture and bone strength in girls with AN and healthy adolescent girls.

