Specific Aim 2B. The goal of this specific aim is to determine prospectively changes in bone microarchitecture and bone strength in girls with AN who receive rhIGF-1 and estrogen therapy (n=50) compared with changes in AN receiving estrogen alone (n=50). Bone microarchitecture will be assessed using HR-pQCT and bone strength using FEA at baseline, six, 12 and 24 months of the study. Our second primary study endpoint is the change in trabecular bone density in the two treatment groups over the course of the study. With 100 subjects (50 in each group) we will have an 80% chance of detecting a significant difference ($p=0.05$ two sided) in change in trabecular bone density in girls with AN who receive rhIGF-1 and estrogen compared with estrogen alone if the true relative change is 3.5% over the 12 month period. This assumes a standard deviation of relative change of 6%, as was found in the group of AN women who gained weight in a study by Milos *et al* (39). To understand the clinical meaning of such a change we note that AN women had a 20% decrease in trabecular bone density compared to normal women. The analysis will be accomplished using a longitudinal mixed model ANOVA with a random patient and time (slope) effect. The measure of interest will be the group time interaction. We estimate a 20% dropout rate based on our previous study. A secondary analysis will be a joint model with weight gain as described for Specific Aim 1. We will also compare changes in total cross-sectional area, cortical thickness, TbN, TbTh and TbSp between AN receiving rhIGF-1 and estrogen with AN receiving estrogen alone. Although this is not a specific aim, it will be interesting to compare the changes in BMD with the change in bone strength. An issue is that BMD and bone strength are measured in different units. In order to make the comparisons understandable, we will transform both to percent predicted using the data from healthy adolescent girls. Then we will fit a joint model for both measurements to assess the relationship between the two and which measure is affected most by treatment. In addition, we will examine these endpoints 12 months after stopping therapy to determine whether effects persist after discontinuing combination therapy. When comparing with healthy adolescent girls, we will adjust for multiple comparisons. Both unadjusted and multiplicity adjusted analyses will be presented.

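### Aim 1B compares post-treatment PINP and CTX levels with no baseline term, although both markers are measured at baseline, so precision available at no cost is given up

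*SAP*

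**What the plan says.** SAP Specific Aim 1B analyses PINP and CTX in the two randomised arms (50 girls each) "at 3, 6, 9 and 12 months using a repeated measures ANOVA". The contrast is then fixed: "The primary planned analysis will be the difference in mean levels by treatment group during the 3, 6, 9 and 12 month observations". Baseline is not one of the listed time points, and neither a covariate nor a change score is named.

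The baseline values will exist. The protocol's Baseline Visit list, item (i), reads "Bone Turnover Markers: Serum for PINP and C-telopeptide (CTX". The 6- and 12-month visits "will include all the baseline procedures but the bone age x-ray", and the 3- and 9-month list has "Bone turnover markers and hormones" as item (f). Each girl who completes the study therefore gives one pre-treatment and four on-treatment values of each marker.

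Two other places in the SAP might have supplied the missing term, but neither does:

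- **Specific Aim 1A**, after the BMD power calculation: "The same model can be used with covariates and possible mediators of treatment effects". The model meant is the BMD model, the wording is permissive, and the examples that follow do not include baseline marker levels.
- **Specific Aim 2B**: "The analysis will be accomplished using a longitudinal mixed model ANOVA with a random patient and time (slope) effect". This is the HR-pQCT analysis.

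**The concern.** In a randomised comparison of a continuous outcome that is also measured before treatment, the baseline value is usually the most useful covariate. Leaving it out keeps the treatment effect unbiased, but stable differences between girls remain in the error variance, and any chance imbalance at baseline goes uncorrected.

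This matters here for two reasons. First, Aim 1B is where the trial tests its mechanism. Item A of the additional prospective aim in the protocol's Specific Aims asks whether the combination "Stimulates bone formation through an IGF-1 mediated anabolic effect", and SAP Specific Aim 2C later treats P1NP as a possible mediator of the treatment effect. Second, the sample size was set for spine BMD and trabecular density only, and no power is stated for the markers. Their precision is whatever 50 girls per arm, less dropout, happens to give. A null marker result from an inefficient analysis would be hard to interpret.

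Aim 1B is also silent on girls who miss some marker visits, with 20% dropout expected. If a classical repeated measures ANOVA is meant, a girl with any missing visit drops out of the analysis altogether.

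**Working it through.** The plan gives no SD, correlation, effect size or power for the markers, so there is no figure of its own to reproduce. The gain is worked out in units of the SD of one marker measurement, under stated correlations.

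**Inputs from the documents.** Four follow-up visits (SAP Aim 1B). 50 girls per arm (SAP Aim 1B). 20% dropout, so 50 × 0.8 = 40 per arm (protocol, Research Design and Methods). Two-sided 0.05 and 80% power are stated for Aims 1A and 2B and assumed to apply here.

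**Formulas.** Let vp be the variance of a girl's mean over the four follow-up visits, and c the average correlation of baseline with those visits. Adjusting for baseline leaves va = vp − c². The proportional cut is c²/vp. The detectable difference is (1.960 + 0.842) × √(2v/n).

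**(a) Equal correlation ρ among all five visits.** Then vp = (1 + 3ρ)/4 and c = ρ.

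| ρ | vp | va | Cut | Detectable, 50 per arm | Detectable, 40 per arm |
|---|---|---|---|---|---|
| 0.3 | 0.475 | 0.385 | 19% | 0.39 → 0.35 | 0.43 → 0.39 |
| 0.5 | 0.625 | 0.375 | 40% | 0.44 → 0.34 | 0.50 → 0.38 |
| 0.7 | 0.775 | 0.285 | 63% | 0.49 → 0.30 | 0.55 → 0.33 |
| 0.8 | 0.850 | 0.210 | 75% | 0.52 → 0.26 | 0.58 → 0.29 |

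For an effect that the planned analysis would detect with 80% power, the adjusted analysis has 87.5%, 95% and 99.6% power at ρ = 0.3, 0.5 and 0.7. A simulation of 4,000 trials at ρ = 0.5 with 40 per arm gave 78% power unadjusted and 94% adjusted, a variance ratio of 0.61 (formula: 0.60), and no bias in either estimator.

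**(b) Correlation that decays with time.** With correlation r between visits three months apart, and r to the power (lag in months ÷ 3) otherwise, the cut is 11%, 29%, 45% and 68% for r = 0.5, 0.7, 0.8 and 0.9.

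**(c) Baseline less tied to follow-up than follow-up visits are to each other.** With 0.7 between follow-up visits and 0.3 with baseline, vp = 0.775 and va = 0.775 − 0.09 = 0.685, a cut of 12%. An effect with 80% power unadjusted then has 85%. If the correlation with baseline is only 0.2, the cut is 0.04/vp: 10% when follow-up visits also correlate at 0.2 (vp = 0.40), and 5% when they correlate at 0.8 (vp = 0.85).

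**Why a covariate and not a change score.** Under (a) the variance of change from baseline is vp + 1 − 2ρ. At ρ = 0.3 this is 0.475 + 0.4 = 0.875, worse than making no adjustment (0.475). At ρ = 0.5 it equals the unadjusted 0.625. The covariate-adjusted variance is never above the unadjusted one, apart from the single degree of freedom.

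**Side calculation for BMD.** Aims 1A and 2B already use the baseline scan through the random intercept and slope. If the Aim 1A model fits separate arm intercepts (not stated), a common baseline mean would sharpen it slightly. I used the SAP's components (variances 0.01056 and 0.001523, covariance −0.001, residual 0.000533), scans at 0, 6 and 12 months, and a slope difference of 0.03:

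- All dropout after month 6: SE 0.01078 → 0.01034, power 79.5% → 82.6%.
- Dropout split equally before and after month 6: SE 0.01102 → 0.01061, power 77.7% → 80.7%.

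The variance falls by 7–8%. The SAP gives no components from which to do the same for HR-pQCT.

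**The case against.** The strongest reply is that Aim 1B is brief and silent, and silence does not rule out a baseline covariate. The contrast is valid as it stands, the markers are not a primary endpoint, and the size of the gain is assumed throughout.

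The equal-correlation cases may also be favourable for this trial. Both arms start estrogen after the baseline draw, so baseline is the only untreated sample. Blood may be taken fasting or two hours after food, and non-local girls may have marker samples drawn offsite. Each of these could weaken the link between baseline and follow-up and move the trial towards case (c).

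Much of this stands. The issue is efficiency and not validity, it concerns a mechanistic aim, and the gain could be near 10% or somewhat less. It does not remove the point. The SAP specifies the time points and the contrast for this aim and includes no baseline value, so the analysis as written does not use it. If the statistician intends to adjust anyway, saying so costs nothing and avoids a later choice between adjusted and unadjusted results. Handling of missing visits is a separate gap, but one model statement settles both. The BMD refinement is optional, and nothing here depends on it.

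**Conclusion.** The concern holds. As written, the main PINP and CTX comparison makes no use of baseline samples that the trial collects, and no other part of the SAP supplies the adjustment.

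The omission itself is certain; the size of the loss is not. It depends on correlations that the documents do not give. The variance cut runs from about 11–12% (quickly decaying correlation, or a weak link to baseline) to 63–75% (markers that track strongly within a girl). It falls to 5–10% if baseline correlates with follow-up at only 0.2. A common correlation of 0.5 gives 40%, the same precision as 40 per arm from 24 (40 × 0.6).

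The change should be made, but the trial's main conclusions do not rest on it.

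**What to change.** In SAP Specific Aim 1B, state that PINP and CTX at 3, 6, 9 and 12 months, log-transformed if skewed, are analysed with a likelihood-based mixed model using all available visits. The terms are treatment, visit, treatment by visit, and the baseline value of the same marker as covariate. Keep the primary contrast for this aim as the arm difference averaged over the four visits.

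The cost is one or two sentences, slightly different model code and one degree of freedom per marker. It needs no new data, visits or samples.

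Optional for Aims 1A and 2B: keep the random intercept and slope model and constrain the two randomised arms to a common baseline mean. Baseline then stays in as an outcome and must not also be entered as a covariate.

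### Aim 2A names the equal-variance Student t test for 100 AN girls against 36 controls; with groups this unequal, it is miscalibrated whenever the SDs differ, and naming Welch costs almost nothing

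*SAP*

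**What the plan says.** SAP, Specific Aim 2A, compares HR-pQCT endpoints and FEA bone strength between 100 girls with AN and 36 healthy adolescents. The test is chosen as follows: "We will use the Student t test when variables are normally distributed or when transformations can be performed to approximate a normal distribution". Variables that fail this condition go to a rank-based fallback, with Wilcoxon named as an example. The only condition is normality. The text mentions no variance check and no unequal-variance version, and it describes no confidence intervals for this aim.

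The SDs come from a small pilot: "Our preliminary data indicate lower trabecular bone density in 8 girls with AN compared with 6 controls", with values of "162 ± 27 vs. 209 ± 36 g/cm³" and p=0.02. From these the plan states more than 99% power for a difference "between the groups at an alpha level of 0.05". Sidedness is not given for this aim. I take it as two-sided, as in Specific Aim 1A ("detecting a significant (p=0.05 two sided) difference in change in lumbar spine BMD").

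**The concern.** The Student t test uses one pooled variance, which the larger group dominates. With equal group sizes, unequal SDs do little harm. Here the groups stand at about 2.8 to 1, so that protection is lost. If the smaller group has the larger SD, the standard error is too small and the test rejects too often. If the larger group has the larger SD, the test is conservative. The plan's only data show the first pattern: an SD of 36 in the group planned at 36, and 27 in the group planned at 100.

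At stake is whether a finding of abnormal bone in AN carries the stated error rate. Trabecular density differs so much that the choice of test does not matter. The choice could matter for endpoints with smaller differences at the radius and tibia. Under the Protocol (Research Design and Methods) controls attend only the screening and baseline visits, so a baseline comparison of this kind is the one their data directly support.

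**Working it through.** **Inputs** (SAP, Specific Aim 2A): n = 100 and 36; pilot 162 ± 27 (n=8) and 209 ± 36 (n=6), difference 47; alpha 0.05, taken as two-sided.

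**1. The plan's own figures.**
- Pilot p, pooled: variance (7×27² + 5×36²)/12 = 965.25; SE = √(965.25×(1/8 + 1/6)) = 16.78; t = 47/16.78 = 2.80 on 12 df; p = 0.016, which rounds to the stated 0.02.
- Pilot p, Welch: SE = √(27²/8 + 36²/6) = 17.52; t = 2.68; p = 0.025.
- Reading the ± values as standard errors gives p = 0.31, so they are SDs.
- Power for a difference of 47 at n = 100 and 36 exceeds 99.9% with either test. The stated figure holds.

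The stated p fits the pooled test better, in line with the usual meaning of the test's name.

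**2. Standard errors at the planned sizes, pilot SDs.**
- Pooled variance: (99×27² + 35×36²)/134 = 877.1, SD 29.6.
- Pooled SE: √(877.1×(1/100 + 1/36)) = 5.76.
- True SE: √(27²/100 + 36²/36) = √43.29 = 6.58. Ratio 5.76/6.58 = 0.875.
- Welch df: 43.29²/(7.29²/99 + 36²/35) = 49.9.
- 95% half-width: 11.38 pooled, 13.22 Welch. 11.38/13.22 = 0.861, so the pooled interval is 13.9% narrower.

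**3. Actual size of the nominal 5% test.** Large-sample: 2×(1 − Φ(1.978×0.875)) = 8.4%. Simulation of 2,000,000 null data sets per row:

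| SD in AN / SD in controls | Student | Welch |
|---|---|---|
| 27 / 36 (pilot) | 8.6% | 5.0% |
| 27 / 33 | 7.4% | 5.0% |
| 27 / 30 | 6.2% | 5.0% |
| equal | 5.0% | 5.0% |
| 36 / 27 (reversed) | 2.5% | 5.0% |
| log scale, 0.166 / 0.171 | 5.3% to 5.4% | 5.0% |

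The log-scale row rests on the coefficients of variation, which are nearly equal: 27/162 = 16.7% and 36/209 = 17.2%. The log SD is taken as √ln(1 + CV²), a lognormal approximation.

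**4. How well the SD ratio is known.** F = (36/27)² = 1.78 on 5 and 7 df, two-sided p = 0.47. The 95% interval for the SD ratio (controls to AN) is 0.58 to 3.49. Across it, the size of the Student test runs from about 1% to about 20%.

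**5. Cost of Welch when variances are equal.** With both SDs at 29.6 and an illustrative difference of 15, power is 73.4% for Student and 72.7% for Welch.

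**The case against.** The strongest reply is that the pilot SDs may differ only because the means differ. A type I error rate applies when the means are equal, and the 8.5% carries over SDs seen where the means are 47 apart. With near-equal coefficients of variation, equal means would imply nearly equal SDs and a size close to 5%. The plan also allows transformation, and on the log scale the problem almost vanishes. This stands as a fair reading of the same data. Its limits are that the plan triggers transformation by non-normality, not by unequal variance, and that 14 girls cannot establish a constant coefficient of variation.

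Second, the inequality of variances is not established, and even its direction is open. This stands too, and it rules out two readings that a reader might take from the pilot figures. One is that Aim 2A will in fact run at 8.5%: that figure holds only if the pilot SDs hold under the null on the raw scale. The other is that every HR-pQCT and FEA comparison will be too liberal. The documents give SDs for trabecular density alone, and an endpoint with the larger SD in AN would be tested conservatively.

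Third, the plan does not use the word pooled, and it specifies no intervals for this aim. The equal-variance reading rests on convention and on the pilot p-value. The 14% describes an interval that would go with the test.

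Fourth, the aim is cross-sectional and non-randomised. That is correct and limits the stakes. None of these replies argues for keeping the Student test: doubt about the variance ratio is the reason to name a test that does not depend on it.

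**Conclusion.** The point holds as a conditional one. At 100 against 36, the named test keeps its 5% level only if the SDs are equal. Under the pilot SDs on the raw scale its size is about 8.5% (8.4% large-sample, 8.6% simulated), and its interval is about 14% narrower than Welch's. With the SDs reversed the size is about 2.5%, and on the log scale with spread proportional to the mean it is about 5.3%. For the other HR-pQCT and FEA endpoints, neither the size nor the direction of the error can be derived from the documents.

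The results assume normal data, two-sided testing and full enrolment. The trabecular density conclusion, the >99% power statement and the primary randomised comparisons, which use mixed models, do not change. This is a free improvement, not a flaw that threatens the trial's conclusions.

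**What to change.** In SAP Specific Aim 2A, replace the Student t test by the Welch (unequal-variance) t test, without a preliminary test of variances. This is a one-line change. It needs no extra subjects and leaves the stated power above 99%. In the equal-variance example it costs 0.7 percentage points of power (73.4% to 72.7%).

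Changing the rank-test fallback is optional. Under the pilot SDs the Wilcoxon test ran at about 6.5% to 7.1% and the Brunner-Munzel test at about 4.8% to 5.3%. The SAP offers Wilcoxon only as an example, so the choice is a matter of preference.
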